9.6.1 Assessment of the Capacity to Consent	
9.6.2 Waiver of Assent	
9.7 PAYMENT TO SUBJECTS/FAMILIES	28
10 PUBLICATION	29
11 REFERENCES	29
Appendix	30

ABBREVIATIONS AND DEFINITIONS OF TERMS

AE Adverse event

ASD Autism Spectrum Disorder CAR Center for Autism Research

PSM Police Safety Module

VR Virtual Reality

ABSTRACT

Context: (Background)

Individuals with autism spectrum disorder (ASD) have core impairments in social communication skills that typically persist into adulthood and result in challenges related to independence, employment, and emotional wellbeing. Given the increased prevalence of ASD diagnoses in childhood and the noted challenges with community living skills seen in adults with ASD, it is critical to develop effective and easily accessible programs to support social skills in adolescents and adults with ASD. Advances in virtual reality (VR) technology offer new opportunities to design interventions targeting the core deficits associated with ASD and promote acquisition of skills necessary for effective navigation of challenging social situations, such as engagement with law enforcement.

Objectives: (primary and important secondary objectives)

The primary objective of this study is to demonstrate the efficacy of Floreo's PSM in adolescents and adults with ASD by assessing improvement in police interaction skills as compared to a video modeling intervention in a laboratory setting. A secondary objective is to demonstrate the virtual-based efficacy of Floreo's PSM in adolescents and adults with ASD by assessing improvement in police interaction skills as compared to a treatment-as-usual condition, in virtual video conferencing settings using CHOP-based staff as treatment implementers.

Study Design:

This is a randomized control trial in which an immersive VR module is intervention being evaluated.

Setting/Participants:

Cycle A of the study will be conducted at the Center for Autism Research at CHOP. Cycle B of the study will be conducted virtually using CHOP approved, HIPPA compliant video conferencing software. Subjects aged 12 to 60 years with ASD are eligible to participate.

Study Interventions and Measures:

The study intervention is an immersive VR police safety module. The main outcome measures are a police interaction assessment and a police knowledge assessment.

TABLE 1: SCHEDULE OF STUDY PROCEDURES

Study Phase	Screening	Cycle A			Cycle B			
Visit Number		1	2	3	1	2	3	4
								4 weeks post-intervention
Informed Consent/Assent	X	X			X			
Review Inclusion/Exclusion Criteria	X	X			X			
Screening Interview	X							
IQ Testing		X			X			
Behavioural Testing and Questionnaires		X	X	X	X	X	X	X
Baseline Assessment		X			X			
Virtual Reality Sessions		X	X	X	X	X	X	X
Police Interaction Assessment				X			X	X

•

1 BACKGROUND INFORMATION AND RATIONALE

1.1 Introduction

Individuals with autism spectrum disorder (ASD) have core impairments in social communication skills that typically persist into adulthood and result in challenges related to independence, employment, and emotional wellbeing. ASD prevalence is rising, with recent estimates in studies from the Centers for Disease Control and Prevention ranging from 14.6 per 1000 children aged 8 years (Centers for Disease Control and Prevention [CDC], 2016) to 2.24% in children aged 3 to 17 years (Zablotsky *et al.*, 2015). Given the increased prevalence of ASD diagnoses in childhood and the noted challenges with community living skills seen in adults with ASD, it is critical to develop effective and easily accessible programs to support social skills in adolescents and adults with ASD.

Advances in virtual reality (VR) technology offer new opportunities to design interventions targeting the core deficits associated with ASD and promote acquisition of skills necessary for effective navigation of challenging social situations, such as engagement with law enforcement. Researchers have explored the potential of virtual reality technology in targeting autism-related deficits (Parsons and Cobb, 2011), but at this time there are no evidence-based VR interventions for ASD. While most research labelled VR for the purposes of therapy has not been immersive, in recent years, the commercial introduction of head-mounted displays (HMD) and lower cost of virtual reality technology have led to greater interest in therapeutic applications of VR. As part of a mission to develop VR products for individuals with ASD, we will collaborate with a commercial tech start-up company, Floreo Technology, to study a mobile VR module for police safety skills. The project will evaluate the safety and feasibility of the mobile VR police safety module (PSM) and the effectiveness of the module in improving police interaction skills in adolescents and adults with ASD with mid-range to high-functioning intellectual abilities.

1.2 Name and Description of Investigational Product or Intervention

Floreo's virtual reality (VR) application provides immersive and engaging therapy intended to help individuals with ASD build real world skills. If proven effective, the application would be an affordable supplement to traditional therapy that is fun and engaging for the user, while allowing a supervising adult to monitor and guide the activities.

Floreo's Police Safety Module (PSM) will offer a supervised VR experience for individuals with ASD. The software will be a downloadable application that provides a three-dimensional immersive scene for headset-compatible smartphones and a supervisory overview that can run on smartphones or tablets. The individual with ASD will use a smartphone capable of running the application with a dedicated headset providing the virtual environment.

1.3 Relevant Literature and Data

Autism spectrum disorder (ASD) is a heterogeneous neurodevelopmental condition with lifelong impact. ASD is characterized by variable degrees of impairment in social communication and

restricted and repetitive patterns of behavior (American Psychiatric Association, 2013). Prevalence has been rising, with recent estimates in studies from the Centers for Disease Control and Prevention ranging from 14.6 per 1000 children aged 8 years (Centers for Disease Control and Prevention [CDC], 2016) to 2.24% in children aged 3 to 17 years (Zablotsky et al., 2015). While much attention has been paid to the pathogenesis and diagnosis of ASD, there remains a clear need for effective treatments for the core symptoms. ASD is a lifelong disorder, persisting into adulthood and resulting in significant challenges for affected individuals.

Adults with ASD experience significant social challenges that impact functional living skills and emotional well-being. Families of young adults initially diagnosed with ASD as preschoolers have noted the persistence of unmet social needs (Eaves and Ho, 2008). A more recent survey of young adults with ASD found that 24% reported social isolation, as well as high rates of anxiety, depression, and attention deficit hyperactivity disorder. In addition, 4 in 10 young adults with ASD were described as disconnected from work and continued education through their late teens and early twenties. Less than 20% of young adults with ASD lived independently (Roux et al., 2015). Researchers have also described age-related declines in social communication (Wallace et al., 2016) and adaptive functioning skills (Pugliese et al., 2015).

Individuals with social communication disabilities like ASD may be particularly susceptible to poor police interaction outcomes due to difficulty reading social cues (American Psychiatric Association, 2013), variable verbal ability (Tager-Flusberg & Kasari, 2013), heightened anxiety (Sukhodolsky et al., 2008), and reduced executive control (Blijd-Hoogewys et al., 2014). The presence of intellectual disability (ID) is associated with greater risk of injury during police interactions (Perry & Carter-Long, 2016), and approximately 30% of individuals with ASD also have ID (CDC, 2012). Rava et al. (2017) reported that elevated externalizing behaviors in U.S. teens with ASD are associated with police contact. Similarly, Tint et al. (2017) reported that instances of aggressive behavior are the most common cause of contact between police and Canadian adults with ASD.

Existing intervention approaches relevant to interactions with law enforcement for individuals with ASD have not been shown to be effective. The effort to promote optimal social and community living skills in young adults with ASD has led researchers to investigate strategies such as story-based interventions and video modeling. Social StoriesTM is the most well-known story-based intervention. While a systematic review of Social StoriesTM found positive benefits for various social outcomes (Karkhaneh et al., 2010), a meta-analysis found Social StoriesTM to be of limited effectiveness in addressing social difficulties (Kokina and Kern, 2010).

Video modeling intervention was found to be moderately effective (Hong et al., 2016) and described as an evidence-based practice for daily living skills (Hong et al., 2015) for individuals with ASD. BE SAFE The Movie uses a video modeling approach to support more effective interactions between individuals with ASD and law enforcement officers. This program has been used in communities across the country and is featured as a safety resource by Autism Speaks. However, the efficacy and effectiveness of the BE SAFE intervention have not yet been experimentally examined and there are currently no evidence-based programs specifically designed to train police safety skills in individuals with ASD.

New VR technology is promising. Researchers have explored the potential of VR technology in targeting ASD-related deficits (Parsons and Cobb, 2011). However, most research labelled VR for the purposes of therapy has not been immersive (Lahiri et al., 2015; Didehbani et al., 2016; Josman et al., 2008). An immersive VR experience gives the user the feeling of being inside a virtual world, and offers an environment in which users can try out experiences that are hard to stage or replicate in real life. In recent years, the commercial introduction of head-mounted displays (HMD) and lower cost of VR technology have led to increased use by the public as well as greater interest in therapeutic applications of VR. These new advances in VR technology offer opportunities to design interventions targeting the core deficits associated with ASD and promote progress toward optimal functional outcomes. Given the increasing prevalence of ASD in the population, and the impact of persisting deficits in social communication and daily living skills in adults with

ASD, it is critical to develop innovative means of providing support to individuals with ASD. Consistent with this, the most recent National Standards Project from the National Autism Center, released in 2015, describes "Technology-based Intervention" as an Emerging intervention, warranting additional research (National Autism Center, 2015).

1.4 Compliance Statement

This study will be conducted in full accordance all applicable Children's Hospital of Philadelphia Research Policies and Procedures and all applicable Federal and state laws and regulations including 45 CFR 46 and HIPAA. All episodes of noncompliance will be documented.

The investigators will perform the study in accordance with this protocol, will obtain consent and assent (unless a waiver is granted), and will report unanticipated problems involving risks to subjects or others in accordance with The Children's Hospital of Philadelphia IRB Policies and Procedures and all federal requirements. Collection, recording, and reporting of data will be accurate and will ensure the privacy, health, and welfare of research subjects during and after the study.

2 STUDY OBJECTIVES

The overall objective of the proposed project is to demonstrate a satisfactory safety profile, feasibility, and efficacy of a unique mobile VR application for police safety skills in adolescents and adults with ASD. Safety and feasibility was found to be acceptable under a separate protocol (#14194), while this phase of the project will involve ongoing research and development including laboratory-based efficacy and virtually-based efficacy studies. This study will involve further development of the PSM, including greater complexity of the virtual environment and greater diversity of police interaction options.

2.1 Primary Objective (or Aim)

The primary objective of this study is to demonstrate the efficacy of Floreo's PSM in adolescents and adults with ASD by assessing improvement in police interaction skills as compared to a video modeling intervention and a treatment-as-usual condition.

2.2 Secondary Objectives (or Aim)

The secondary objective is to demonstrate the efficacy of Floreo's PSM in adolescents and adults with ASD by assessing improvement in police interaction skills as compared to a treatment-as-usual condition under virtual implementation.

3 INVESTIGATIONAL PLAN

3.1 General Schema of Study Design

3.1.1 Screening Phase

Potential subjects will be screened using a screening interview that reviews the protocol's requirements, and inclusion/exclusion criteria. Questions about level of functioning will be included to provide an estimate of IQ. In the case of a reported grade level discrepancy greater than one year, potential subjects will be asked to provide the most recent IEP evaluation in order to review IQ scores and estimate current IQ. Medical and/or research records will be reviewed to document ASD diagnosis.

Informed consent (if adult) or parental/guardian permission (if child or adult with diminished capacity) and, if applicable, assent, will be obtained prior to any study related procedures being performed, including IQ testing to confirm that subjects meet this inclusion criterion.

3.1.2 Cycle A – Laboratory-Based Efficacy Study

In the first year of the study, an efficacy study will be conducted at the Center for Autism Research. Subjects will be randomized to the VR intervention or to the video modeling control condition (with stratification, see *Study Procedure*). Subjects in each condition will undergo a baseline assessment of police interaction skills via a live role play with a study staff member and three sessions of their assigned intervention within an approximately six-week period. At the end of Visit 3, subjects' police interaction skills will be assessed via a live interaction with a police officer.

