3.1.3 Cycle B – Virtually-Based Efficacy Study

In the second year (after the completion of Cycle A), a virtually-based efficacy trial will be conducted by CHOP staff via videoconference. Subjects will be randomized to the VR intervention or to the treatment-as-usual condition (with stratification, see *Study Procedure*). Subjects in each condition will undergo a baseline assessment of police interaction skills via a novel pre-/post-intervention assessment and three sessions within an approximately six-week period. At the end of Visit 3, subjects' police interaction skills will be assessed. There will be an additional follow-up visit approximately 4 weeks post-training, for all participants, to readminister outcome measures, as an assessment of maintenance of learning.

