4.2 Characterization Visits

- Informed Consent, and assent if appropriate
- IQ testing (completed at first visit)
- ASD diagnostic testing (completed at any of the 3 intervention study visits in Cycle A only)
- Self-report measures
- Parent-report questionnaires
- Stratified randomization to either the VR intervention or to the video modeling control condition
- Medical or Research Record Review

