4.3 Intervention Visits

- Baseline Assessment
- VR or video modeling session
- Pre and post-intervention Police Knowledge Assessment
- Police Interaction Assessment at the end of Visit 3
- Floreo Feedback Questionnaire following the Police Interaction Assessment (Cycle B)
- Debriefing

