5.4 Efficacy Evaluations

5.4.1 Baseline Assessment

5.4.1.1 Cycle A

Before beginning the first VR or video modeling intervention session, all participants will complete a baseline assessment of police interactions skills via a live role play of a police interaction with a study staff member. These interactions are designed to measure each participant's ability to interact with a police officer prior to completing either intervention. The study staff member will be provided with a semi-structured set of prompts to use when interacting with the participant. The interaction is designed with guidance from law enforcement officers with particular experience working with individuals with intellectual and developmental disabilities. The live interaction will be video-recorded via a videoconference platform. These recordings will be coded for a set of behaviors that would encourage successful police interactions (i.e.: making appropriate eye contact, etc.)

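### The plan describes randomization before the Baseline Assessment and the knowledge pre-test, and nothing keeps participants or session staff unaware of the arm until both are done

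*Combined protocol and SAP*

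**What the plan says.** **Design narrative.** Section 3.1.2 (Cycle A) states "Subjects will be randomized to the VR intervention or to the video modeling control condition" and then "Subjects in each condition will undergo a baseline assessment of police interaction skills via a live role play with a study staff member". Section 3.1.3 (Cycle B) has the same sequence; after its randomization sentence it says "Subjects in each condition will undergo a baseline assessment of police interaction skills via a novel pre-/post-intervention assessment".

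**Procedure lists.** Section 4.2 (Characterization Visits) contains the item "Stratified randomization to either the VR intervention or to the video modeling control condition", which names only the Cycle A comparator. Section 4.3 (Intervention Visits) opens with the Baseline Assessment and also lists "Pre and post-intervention Police Knowledge Assessment".

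**Timing.** The only explicit rule for the baseline is in section 5.4.1.1: "Before beginning the first VR or video modeling intervention session, all participants will complete a baseline assessment of police interactions skills". Section 5.4.1.2 repeats it for Cycle B. Section 6.3.2 places randomization at Visit 1, and Table 1 places the Baseline Assessment at Visit 1. Table 1 has no row for randomization.

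**Blinding.** Section 9.1.2 blinds the confederates in the baseline and outcome interactions and the coders. It does not mention participants, caregivers, the staff who run the sessions, or whoever scores the knowledge test.

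**Use of the baseline.** Sections 6.1 and 6.3.2 make change from baseline one part of the primary endpoint. For Cycle B, section 6.3.2 describes only the baseline-to-outcome comparison between arms. Change in the knowledge score is a secondary endpoint (6.2).

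**The concern.** A baseline taken after allocation is safe only if the people who can influence it do not know the arm. Here the score is the participant's own behavior, so a blinded coder faithfully records whatever extra effort, disappointment or anxiety the participant brings. The contrast is sharpest in Cycle B, where one arm is trained with the module and the other receives no such training. In that cycle the baseline is a headset experience run remotely, and it is not clear that the word used for confederates in section 9.1.2 covers the staff who run it.

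Any such difference at baseline enters a change score in full and with the opposite sign. It could also reach the post-treatment comparison through covariates. Section 6.3.1 adjusts for any baseline characteristic that differs significantly between groups, and section 6.4 names intake knowledge of police interactions as a possible covariate.

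**Working it through.** **1. Is there a plan figure to reproduce?** None bears on the order of events. The only power figures, critical t = 1.99 and d = .74 in section 6.4, reproduce with 48 per arm, two-sided 5% and 95% power (t = 1.986, d = 0.743). The same section gives 48 per study, which is 24 per arm if allocation is 1:1 (the ratio is not stated). That mismatch is a separate matter. I use 24 per arm below.

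**2. Order of events, passages side by side.**

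| Place | What it implies |
|---|---|
| 3.1.2 and 3.1.3 | Randomization, then baseline in subjects described by condition |
| 4.2, then 4.3 | Randomization in the earlier list; baseline and knowledge pre-test in the later one |
| 9.1.2 | Baseline confederates are blinded to condition, a precaution needed only if a condition may already exist |
| 5.4.1.1 and 5.4.1.2 | Baseline before the first session; fits either order |
| 6.3.2 and Table 1 | Both events at Visit 1; order within the visit not given |

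The first three rows point the same way, the last two are neutral, and nothing states the reverse.

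**3. Size of a possible bias.** The documents give no inputs, so these are assumptions:
- Knowing the arm makes the baseline means differ by δ = 0.1 to 0.3 SD.
- The shift affects the baseline only and does not persist to the outcome.
- Pre and post scores have equal SD (1 unit) and correlation ρ = 0.3 to 0.7.
- There is no true treatment effect.

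Bias of each estimate:
- Change score: 0 − (−δ) = δ
- Baseline-adjusted difference: 0 − ρ(−δ) = ρδ
- Unadjusted post-treatment difference: 0

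The residual SD is √(2(1 − ρ)) for change and √(1 − ρ²) for the adjusted analysis. The chance of a false finding in the biased direction (nominal 2.5%) comes from a noncentral t with 46 df, critical value 2.013 and noncentrality (bias/SD) × √(24/2).

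- Smallest case, ρ = 0.3 and δ = 0.1. Change: 0.1/√1.4 = 0.0845, × 3.464 = 0.293, giving 4.7%. Adjusted: 0.03/√0.91 = 0.0314, × 3.464 = 0.109, giving 3.2%.
- Largest case, ρ = 0.7 and δ = 0.3. Change: 0.3/√0.6 = 0.387, × 3.464 = 1.342, giving 25.9%. Adjusted: 0.21/√0.51 = 0.294, × 3.464 = 1.019, giving 16.8%.

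| ρ | δ (= change bias) | Adjusted bias | False finding, change | False finding, adjusted |
|---|---|---|---|---|
| 0.3 | 0.1 | 0.03 | 4.7% | 3.2% |
| 0.3 | 0.2 | 0.06 | 8.3% | 4.0% |
| 0.3 | 0.3 | 0.09 | 13.6% | 5.1% |
| 0.5 | 0.1 | 0.05 | 5.3% | 3.9% |
| 0.5 | 0.2 | 0.10 | 10.0% | 5.8% |
| 0.5 | 0.3 | 0.15 | 17.3% | 8.5% |
| 0.7 | 0.1 | 0.07 | 6.4% | 5.2% |
| 0.7 | 0.2 | 0.14 | 13.9% | 9.8% |
| 0.7 | 0.3 | 0.21 | 25.9% | 16.8% |

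**The case against.** The strongest reply is that the order is inferred. Sections 3.1.2 and 3.1.3 are summaries, and a sentence about subjects in each condition may mean only that both arms have a baseline. The lists in section 4 are not chronological. Record review follows randomization in 4.2, although 3.1.1 and 4.1 put it at screening. ASD testing precedes randomization in the list, yet may be "completed at any of the 3 intervention study visits in Cycle A only". This objection stands in part: no single passage fixes the sequence within Visit 1. It does not remove the point, because several places agree and none protects the baseline.

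A reader might go further and infer that participants do know their arm at baseline. No passage says when the arm is disclosed. The baseline task is also common to both arms: the same role play in Cycle A, and a headset for everyone in Cycle B. With confederates and coders blinded, the remaining routes are the participant and unblinded staff.

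Dependence on the baseline is also limited in Cycle A. The hypothesis in 6.3.2 is stated on the post-treatment score, section 6.4 specifies an ANOVA by group for the live interaction data, and the baseline interaction score is not among the covariates listed there. That stands. It leaves Cycle B, the change part of the primary endpoint and the knowledge endpoint exposed.

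Finally, effort and anxiety could pull in opposite directions, so neither the size nor the sign of a bias can be predicted. That stands too.

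**Conclusion.** The point holds as a gap in protection, not as a demonstrated bias. As written, the Baseline Assessment and the knowledge pre-test follow randomization in both cycles, and participants and session staff are not kept unaware of the arm until these are done. The range in the working depends wholly on the assumed shift, correlation and allocation ratio. If the shift persisted to the outcome, the change score would be less affected.

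Three broader readings are not supported:
- **All pre-treatment questionnaires come after randomization.** Section 4.2 lists self-report measures and "Parent-report questionnaires" before the randomization item. Only the knowledge test sits in 4.3.
- **Covariates are collected after treatment has begun.** Table 1 marks a combined row for testing and questionnaires at every visit, but that row need not mean the covariates. IQ is tested at the first visit and gates entry (4.2, 5.1.2), and the sensory measure is described as a trait measure (5.1.5).
- **Subjects will leave on learning their arm and have no baseline.** This needs early disclosure and withdrawal within the same visit, and the documents show neither.

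The change should still be made. It alters conduct rather than only wording, and it removes an avoidable source of bias at almost no cost.

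**What to change.** In sections 3.1.2, 3.1.3, 4.2 and 4.3, set one order for Visit 1:
1. consent
2. IQ eligibility
3. Baseline Assessment and pre-treatment knowledge test
4. randomization and release of the arm
5. first session

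Add a randomization row to Table 1 at that point. If practice already follows this order, the edit only records it.

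No procedure or visit is added, because randomization and baseline already share Visit 1. Sample size, alpha and power do not change. The baseline has only to be performed before the draw, not coded, since section 9.1.1 does not name the baseline score as a stratification variable. The practical cost is that the assignment is drawn later in the same visit, so staff must be ready to deliver either arm. A side benefit is that everyone in the intention-to-treat set of section 6.3.2 will have been through the baseline procedures before allocation.
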